12.1.2 Freedom from Pressure Sensor Failure at 12 Months

The hypothesis is formulated as:

 H_0 : Freedom from pressure sensor failure at 12 months ≤ 0.90

 H_a : Freedom from pressure sensor failure at 12 months > 0.90

where pressure sensor failure is defined in Section 4.4.1.

Template: 86357 Rev. A

Page 36 of 65

Clinical Investigational Plan Template

Sample Size

The CHAMPION Clinical Trial observed 100% freedom from pressure sensor failure at 12 months⁷. The study size of 230 implanted subjects provides at least 85% power to reject the null hypothesis at the significance level of 5% using exact test for a binomial proportion under the conservative assumption that the freedom from pressure sensor failure at 12 months is as low as 95%. The sample size was estimated using PASS 13 (NCSS LLC.).

Subject Group

All subjects who are consented and successfully implanted with a pressure sensor regardless of study completion status will be included in the analyses.

Analysis

The desired outcome is to reject the null hypothesis. Subjects not experiencing pressure sensor failure prior to withdrawal will be treated as not experiencing a pressure sensor failure event. The endpoint will be evaluated using the exact test for a binominal proportion. The null hypothesis will be rejected if the 95% lower confidence bound (LCB) is greater than 0.9.

The freedom from pressure sensor failure at 12 months will also be reported using the Kaplan-Meier method.

12.1.3 Patient Data Transmission Success at 12 Months

Patient data transmission success is defined as percentage of successful transmissions among attempted transmissions.

Subject Group

All subjects who are consented and implanted with a pressure sensor regardless of study completion status will be included in the analysis.

Analysis

All attempted data transmissions through the 12-month visit or death or withdrawal will be included in the analysis. For each subject, the patient data transmission success rate (% of successful transmission) will be calculated as total number of successful transmissions divided by total attempted transmissions within 12 months. The per-subject patient data transmission success rate will be summarized as mean, standard deviation and the 95% confidence interval.

12.1.4 Secondary Endpoint

The secondary endpoint will compare the annualized HF hospitalization rate (including recurrent events) at 12 months post-implant with the rate (including recurrent events) in 12 months prior to implant, using a Cox proportional hazards regression with Anderson-Gill method for recurrent events and frailty to account for within-subject correlation. All follow-up through 12 months post-implant or until subject exits the study will be included in the analysis.

All subjects who are consented and successfully implanted with a pressure sensor, regardless of study completion status will be included in the analysis.

12.1.5 Additional Analyses:

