3.2 ANTICIPATED CLINICAL BENEFITS

The information collected in this clinical investigation will be added to the current knowledge and understanding of treatment options for patients with New York Heart Association (NYHA) Class III heart failure. The anticipated clinical benefit is that the hemodynamic data used by physicians for heart failure management will result in fewer HF hospitalizations. As each HF hospitalization indicates a higher risk for the patient being re-hospitalized, avoiding these hospitalizations may have a favorable impact on the patient's long-term outcome.

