4.2.1 Number of subjects required to be included in the study

A total of 230 subjects will be implanted in the study (refer to section 12.2 (sample size)). Study enrollment will be closed when a total of 230 subjects are implanted.

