4.6.1 Inclusion Criteria

- Indicated to receive a CardioMEMS sensor implant per the CardioMEMS[™] HF System User's Manual
- >18 years of age
- Diagnosis of NYHA Class III Heart Failure at the time of sensor implantation
- Hospitalization for worsening HF within 12 months prior to the CardioMEMS HF System implant. For the purposes of this study, a HF hospitalization is defined as an overnight stay in the hospital with signs and symptoms of congestion requiring intensification of treatment for HF.
- Subjects with reduced Left Ventricular Ejection Fraction (LVEF) must be on stable Guideline Directed Medical Therapy (GDMT)¹⁴ as tolerated
- Written informed consent obtained from subject

Subjects are not eligible for clinical study participation if they meet any of the following exclusion criteria:

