6.9 SUBJECT STUDY COMPLETION

Upon completion of the study, the subject's participation will be considered completed. When the subject's participation in the clinical study has been completed the subject will return to medical care as per physician's recommendation.

6.10 ANY KNOWN OR FORSEEABLE FACTORS THAT MAY COMPROMISE THE OUTCOME OF THE CLINICAL STUDY OR THE INTERPRETATION OF THE

Template: 86357 Rev. A

Page 28 of 65

Clinical Investigational Plan Template

RESULTS

All foreseeable factors that may compromise the outcome have been taken into account by clinical study design and well defined subject selection criteria.

Subject recruitment and retention will be monitored throughout the study and include (but are not limited to) the following activities: evaluation of the site and investigators, training of site personnel, and developing site support materials.

6.11 DESCRIPTION OF THE METHODS THAT WILL BE USED TO ADDRESS POTENTIALLY CONFOUNDING FACTORS IN THE CLINICAL STUDY DESIGN

This is a single arm study so there are no known confounding factors to be addressed for the primary safety endpoints and the primary clinical performance endpoint. The study design of using subjects serving as their own controls and within-subject comparisons of outcomes during 12 months following implant in the study and outcomes during 12 months prior to implant using frailty model accounts for unmeasured confounding factors for the secondary endpoint.

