Appendix I. Additional detail regarding sample size calculations

Sample Size for Safety to Demonstrate Superiority to Performance Goal

Freedom from device / system-related complication (CHAMPION reported 0.986)

Numeric Results for testing H0: P = P0 versus H1: P > P0 Test Statistic: Exact Test

	F	Proportion	Performance Goal Proportion				
Power	N	Given H0 (P0)	Given H1 (P1)	Target Alpha	Actual Alpha	Beta	Reject H0 If R ≥ This
0.8631	230	0.8000	0.8700	0.0500	0.0385	0.1369	195
0.8745 0.8850	235 240	0.8000 0.8000	0.8700 0.8700	0.0500 0.0500	0.0402 0.0419	0.1255 0.1150	199 203

Freedom from Sensor Failure (CHAMPION reported 1.00)

Numeric Results for testing H0: P = P0 versus H1: P > P0 Test Statistic: Exact Test

		Proportion	Performance Goal Proportion				
		Given H0	Given H1	Target	Actual		Reject H0
Power	Ν	(P0)	(P1)	Alpha	Alpha	Beta	If R ≥ This
0.8840	230	0.9000	0.9500	0.0500	0.0436	0.1160	215
0.8676	235	0.9000	0.9500	0.0500	0.0350	0.1324	220
0.9043	240	0.9000	0.9500	0.0500	0.0475	0.0957	224

Sample Size Calculations for Heart Failure Hospitalization Rate

The ESC-HF Pilot study showed 29.5% of previously hospitalized patients were rehospitalized for HF by 1 year (see figure below). Since this study included NYHA I and II patients and 24% of the total number of re-hospitalizations were of unknown cause, the actual percent re-hospitalized for NYHA III-only patients is likely to be higher than 29.5%. The CHAMPION study in NYHA III-only patients found that 36.8% of Control patients were rehospitalized for HF by 1 year. Thus the true re-hospitalization rate for European NYHA III patients is likely the same as observed in CHAMPION. Accordingly, the repeat HF hospitalization rate estimates from CHAMPION should serve as good estimates for European patients (Table B). The sample size was calculated using PASS v13.0.10.

Figure A. ESC-HF Pilot Study Results (A.P. Maggioni et al., 2013)

	TREATMENT (270)	CONTROL (280
12 Months	76 (28.2%)	103 (36.8%)

Table B. Sample Size for Effectiveness to Demonstrate Superiority of Treatment to Control Rate

	CHAMPION Treatment Rate at 1	Control Rate at 1 year		Treatment
	Year (Assumes same rate	(Assumes same rate		Sample Size*
Power	in EU Trial)	in EU Registry)	% RRR	(+ 20% W/D)
0.90	0.52	0.75	30.7%	130 (156)
		Registry Rate at 1		
		year		
	EU Treatment Rate at 1 Year	(Assumes worse		
Power	(Assumes worse scenario)	scenario)		Sample Size*
0.90	0.55	0.72	23.6%	234 (281)

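### The shared frailty in 12.1.4 leaves the standard error of the pre/post hospitalization ratio at the Poisson value, so the interval is too narrow if admissions raise short-term risk or a patient's risk changes between years

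*Combined protocol and SAP*

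**What the plan says.** Section 12.1.4 compares the annualized HF hospitalization rate, counting recurrent events, in the 12 months after implant with the 12 months before it, "using a Cox proportional hazards regression with Anderson-Gill method for recurrent events and frailty to account for within-subject correlation". On exposure it adds: "All follow-up through 12 months post-implant or until subject exits the study will be included in the analysis". Section 6.11 relies on the same device, saying that the comparison with "outcomes during 12 months prior to implant using frailty model accounts for unmeasured confounding factors for the secondary endpoint".

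Neither section names a frailty distribution, a robust or clustered variance, or a confidence interval for the ratio. The model-based standard error is therefore an inference: it is what the named method gives when nothing else is specified.

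Three other places bear on the point.

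- Section 3.2, on clustering of admissions: "As each HF hospitalization indicates a higher risk for the patient being re-hospitalized". It gives no size and no time window.
- Section 4.6.1 makes eligibility depend on "Hospitalization for worsening HF within 12 months prior to the CardioMEMS HF System implant", so every pre-implant count is at least one.
- Section 4.2.1 fixes the size: "A total of 230 subjects will be implanted in the study".

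**The concern.** The plan gives the frailty the task of handling within-subject correlation. For a comparison between subjects, a frailty does widen the standard error when counts are overdispersed. Here each subject contributes to both sides of the comparison, and a term common to both sides drops out of it. The interval would then rest on the assumption that, once a fixed patient effect is allowed for, admissions are independent and the patient's underlying risk is the same in both years apart from the common period effect.

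Heart failure admissions may not behave like that. A discharge can be followed by a period of raised risk, and a patient's condition can move between one year and the next. Either would add variance that the model does not see. At stake is the precision claimed for the only secondary endpoint. The bias caused by requiring an admission before implant is a separate matter and is not addressed here.

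**Working it through.** **The plan's own hospitalization figures.** The documents state no standard error or coverage for the 12.1.4 model. The nearest figures are the sample sizes in Appendix I, Table B (one-sample, one-sided Poisson test, alpha 0.025, power 0.90):

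n = ((1.960·√r0 + 1.282·√r1)/(r0 − r1))²

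- Rates 0.75 and 0.52: 129.9, so 130 (stated 130; ×1.2 = 156, as stated).
- Rates 0.72 and 0.55: 236.3, so 237 (stated 234, about 1% lower; 234 × 1.2 = 281, as stated).

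These figures reproduce closely. They use a Poisson variance with the control rate taken as fixed, so they say nothing about clustering.

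**Step 1: the frailty cancels.** Let subject i have frailty u_i, a pre-year count that is Poisson(u_i·λ) and a post-year count that is Poisson(u_i·λ·θ). Given the subject's total, the post-year count is binomial with probability θ/(1+θ), which does not contain u_i. Over all subjects the estimate is log(D_post/D_pre), with

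SE = sqrt(1/D_pre + 1/D_post).

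Fitting the Andersen-Gill gamma-frailty model to simulated data at fixed frailty variances gave:

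| Follow-up | Model SE as frailty variance rises from 0 to 4 | Poisson SE |
|---|---|---|
| Complete | 0.09663 throughout | 0.09663 |
| 20% exit during the post year | 0.0997 to 0.1009 | 0.0997 |

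The result is exact with complete follow-up and within about 1% with exits.

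**Step 2: from missed variance to coverage.** If R is the true variance divided by the model variance, a nominal 95% interval covers 2Φ(1.96/√R) − 1. R = 1.17 gives 93%; R = 1.85 gives 85%.

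**Step 3: coverage by source of clustering.** Each case used 4,000 simulated trials of 230 subjects. Frailty variance, hazard multiplier and time window are assumptions; the documents give none of them. Coverage is for the ratio in the selected population.

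*Stable differences between patients only* (frailty variance 0.01 to 2): 95-96% without the entry rule, 96-97% with it. A separate simulation with the entry rule and 20% exits gave about 94%.

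*Hazard raised for 90 days after each admission, entry rule applied*:

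| Frailty variance | Hazard multiplier | R | Model-based coverage | Subject-robust coverage |
|---|---|---|---|---|
| 0 | 2 | 0.96 | 95.4% | 94.8% |
| 0 | 3 | 1.11 | 94.3% | 95.2% |
| 0 | 4 | 1.25 | 92.2% | 95.0% |
| 0.5 | 2 | 1.12 | 94.2% | 95.4% |
| 0.5 | 3 | 1.37 | 90.9% | 94.6% |
| 0.5 | 4 | 1.53 | 89.2% | 94.7% |
| 1 | 2 | 1.24 | 91.6% | 94.1% |
| 1 | 3 | 1.43 | 90.2% | 95.3% |
| 1 | 4 | 1.82 | 85.6% | 94.6% |

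Without the entry rule the same multipliers give 87-93%. A hazard 2 to 3 times higher for 365 days gives 91-94% without the rule and 94-97% with it. The rule makes pre-year counts less variable than Poisson, which offsets part of the missed variance.

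*Risk that changes between a patient's two years* (extra subject-by-period gamma variance, rates 0.75/0.52): 92-93% at variance 0.25, 88-91% at 0.5, 82-86% at 1, and 72% at 2.

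**Step 4: what it does to an interval.** Take the last row of the table, where the simulated means were 2.57 admissions before and 1.17 after, and treat both as full-year counts. D_pre = 230 × 2.57 = 591 and D_post = 230 × 1.17 = 269, so SE = sqrt(1/591 + 1/269) = 0.0735. The true value is 0.0735 × √1.82 = 0.0992. Around a ratio of 0.455, the interval should run from 0.375 to 0.553 rather than 0.394 to 0.526. In the third row (means 1.74 and 0.51), the standard error is 0.105 against a true 0.105 × √1.25 = 0.117.

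**The case against.** The strongest reply is that the shared-frailty model may be right. Section 3.2 says that an admission indicates higher risk, which describes a marker of a sicker patient at least as well as a cause of the next admission. If it is only a marker, the Poisson standard error is correct. This stands: a reader might infer that the plan contradicts its own model, and the documents do not support that.

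A reader might also turn to Appendix I for proof of harmful clustering. A mean of 0.52 with 28.2% ever admitted is far from Poisson, which would give 1 − exp(−0.52) = 40.5%. A negative binomial fit, (1 + 0.52k)^(−1/k) = 0.718, gives k of about 2.5. But that is the total variation between patients in one year. Only the part not shared with the previous year causes undercoverage, and the figure cannot separate the two. It also combines a crude proportion with an annualized rate, so k would be smaller if exposure were incomplete.

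Nor does the entry rule simply make matters worse; in several event-dependent cases above it brings coverage back to 95% or more.

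Finally, the practical stakes are limited. The secondary objective is to report, 12.1.4 states no alpha, and sections 12.1 and 12.3 tie success to the safety endpoints. A large reduction would survive a wider interval: with an assumed pre-year mean of 1.4, a post-year mean of 0.52 and a true standard deviation of 0.152 (the value when none of the post-year heterogeneity is shared with the pre-year), log(0.52/1.4)/0.152 = −6.5. This lowers the priority. It does not make the stated precision right, because the frailty still does not do the task 12.1.4 gives it.

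**Conclusion.** The point holds in this form. The subject-level frailty does not protect the standard error of the pre/post ratio; it stays essentially at the Poisson value whatever the frailty variance. Whether the interval is then too narrow depends on the source of the clustering. With stable patient differences it is adequate (about 94-97%). If admissions raise the hazard 2 to 4 times for 90 days, coverage is about 86-95% with the entry rule, and strong period-specific variation takes it as low as 72%.

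These sizes rest on assumed inputs. A reader might infer one fixed shortfall, or that any clustering produces one; the documents support neither. Choosing the variance after seeing the data would be open to criticism, so it is worth settling in the plan. The pass/fail result of the study does not depend on it.

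**What to change.** In 12.1.4, state that the reported confidence interval and any p-value for the pre/post ratio use a subject-clustered variance. Any one of these would do:

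- a marginal Andersen-Gill model with a sandwich variance clustered on subject;
- a Poisson GEE with log follow-up time as offset, which gives the ratio of annualized rates directly;
- a bootstrap that resamples subjects.

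Keep the frailty model as a supportive fit.

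In the simulations with the entry rule, the subject-clustered variance covered 93.6% to 95.4% in every scenario, including those where the frailty model was adequate. The cost is one sentence and one program option. The interval will usually be somewhat wider: in the 90-day table by about √R, from no widening (R = 0.96) to about 35% (√1.82 = 1.35).

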12.1.5.1 HF hospitalization or all-cause death

The HF hospitalization or all-cause death rate at 12 months post-implant will be reported using the Kaplan-Meier method.

12.1.5.2 CardioMEMS Usage

For subjects who are successfully implanted, the ability for physicians and study site personnel to use the CardioMEMS HF System will be characterized by follow-up center types:

- Subject is followed by implanting center
- Subject is followed by a central follow up center
- Other type of follow-up

For subjects who are successfully implanted, the following device usage information will be summarized using descriptive statistics by follow-up center types:

- Annualized HF hospitalization rate (including recurrent events) at 12 months compared to the annualized HF hospitalization rate (including recurrent events) for 12 months prior implant
- Number of HF medication changes and reason for the change
- Patient compliance for taking pressure readings (total daily readings divided by total number possible for daily readings as well as total weekly readings divided by total possible weekly readings)
- HF care provider compliance for weekly readings (total weekly readings divided by the total number of possible weeks of readings)

12.1.5.3 Change in Quality of Life (QoL) between baseline and 12 months Quality of life will be measured using the following questionnaires:

- EuroQOL Five Dimensions Questionnaire (EQ-5D)
- Kansas City Cardiomyopathy Questionnaire (KCCQ)
- Patient Health Questionnaire (PHQ-9)

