After discharge, the subject will take daily PA pressure measurements at home, utilizing the CardioMEMS HF[™] System. These measurements will be transmitted via modem to a secure database. Subject compliance will be monitored by the investigator and the sponsor by review of uploaded information on the Merlin.net website.

The investigator or designee will review the PA pressure measurements transmitted from the home monitoring unit. Pressure thresholds are automatically set as described in Appendix E but can be customized to adapt to patient specific needs. These threshold notifications are intended to guide the investigator to review the Merlin.net website. If the PA pressures are elevated or low, the investigator or designee should make medication changes according to the guidelines in Appendix E. The investigator or designee will review the PA pressure measurements on a weekly basis at a minimum and appropriately utilize the information obtained to assist in the clinical management of subjects. Weekly logins to the database will be monitored by the sponsor. Reminders will be sent to the clinical sites if there are no logins noted during the course of a 7-day window. Clinical and technical support will be available to the investigator as needed.

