6.7 EVERY 6 MONTHS THEREAFTER AND UNSCHEDULED VISITS

Visits occurring after the 12 month visit should occur every 6 months until completion of the study (18 months \pm 60 days, 24 months \pm 60 days etc. after the implant). An unscheduled follow-up is defined as a visit that occurs between two scheduled study visits where the subject is examined for either a physician or investigator requested follow-up or for an adverse event. The following assessments will be performed at these visits:

- Adverse event assessment (SAE, ADE, SADE that occurred since the last study visit)
- Heart failure medication review
- Anticoagulant/antiplatelet medication review

- PA pressure measurements may be obtained at the investigator's discretion
- Reporting of any HF hospitalization that have occurred since the subject was last seen

The data collected must be documented by completing the appropriate CRF.

Between study visits, the subject will be followed remotely using the CardioMEMS HF System for the collection of pulmonary artery pressure measurements. Subjects will be instructed to take daily readings and trend data will be reviewed by a healthcare professional experienced in the management of heart failure at least once every 7 days. Medication or treatment regimen changes as a result of PAP data review will be reported.

All telephone contacts between site staff and the subject should be documented using the Subject Contact Log (refer to Appendix K) and the following information should be captured:

- Date of contact
- Reason for contact
- Ability to reach the subject (Call success)
- Name and role of person contacting the patient
- Call outcome (Instructions given) with the reason medication was changed, if applicable (PAP guided or signs and symptoms guided)
- Other action required

Guidelines for Standardized Post-discharge Heart Failure Care

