Appendix E: Management of Hemodynamic Parameters

The CardioMEMS[™] HF System allows intermittent assessment of pulmonary artery systolic, diastolic and mean pulmonary artery pressures. Hemodynamic information obtained by the system should be used for clinical decision making in addition to symptoms, weights or physical examination (traditional markers of volume).

Pulmonary Artery Pressure Ranges:			
PA Systolic	15 - 35 mmHg		
PA Diastolic	8 - 20 mmHg		
PA Mean	10 - 25 mmHg		

Initially, thresholds will be set automatically at normal ranges, which should be the goal of therapy if possible. The physician can adjust the thresholds specifically for each patient. These threshold notifications are intended to guide the physician to review the CardioMEMS HF Website. Every attempt should be made to keep the pulmonary artery pressures within the specified pulmonary artery pressure ranges utilizing the guidelines. In order to clinically manage patient's PA pressures, the physician must review the PA pressure measurements on a frequent basis, for example, some patients may require a daily review of their PA pressure measurements, while some patients may only require a weekly review. All patients should be reviewed at least weekly. The physician or designee has unlimited access to the CardioMEMS HF Website.

An elevation of pressures beyond the patient's pressure ranges should be considered a volume overloaded status and should be managed according to the hyper-volemic guidelines (see below). Diuretics and vasodilators should be adjusted based on the patient's baseline diuretic requirement, knowledge of the patient's prior response to these agents, and clinician judgment to accomplish the pressure goals set forth in this guideline.

A decrease in the pulmonary pressures below the patient's pressure ranges should be considered a volume depletion event and managed according to the hypo-volemia guidelines (see below). Diuretic therapy should be held and the chronic dose should be lowered. In addition to these specific guidelines, the physician should also incorporate the recommendations set forth in the latest ESC Guidelines on Acute and Chronic Heart Failure (Reference European Heart Journal (2012) 33, 1787–1847).

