- If subject had signs and symptoms of poor perfusion (cold) in addition to being hypovolemic:
 - a. Consider admission if clinical evidence suggests need for IV fluid repletion, telemetry monitoring or the use of IV therapeutic agents
 - b. Consider invasive hemodynamic monitoring for determination of Cardiac Output, if indicated

Template: 86357 Rev. A

Page 49 of 65

Recommended Frequency of CardioMEMS HF System Review

Subject Status	Weekly	At least 2– 3 times per week until optivolemic	At least 2 – 3 times per week until pressure stabilizes
Acceptable PA Pressure (Opti-volemic)	Х		
Elevated PA Pressure (Hyper-volemic)		Х	
Low PA Pressure (Hypo-volemic)		Х	
Medication modifications			Х
Significant deviations in trend data			Х

Costanzo et al, J Am Coll Cardiol HF 2015; Adamson et al, J Card Fail 2011;17:3-10.

Template: 86357 Rev. A

This confidential document is the property of St. Jude Medical and shall not be reproduced, distributed, disclosed or used without the express written consent of St. Jude Medical

Clinical Investigational Plan Template

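### As written, HF care provider compliance in 12.1.5.2 is the patient's weekly-reading compliance under another label and contains no provider action

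*Combined protocol and SAP*

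**What the plan says.** Section 12.1.5.2 (CardioMEMS Usage) lists items to be summarized descriptively by follow-up center type: implanting center, central follow-up center, or other. Two adjacent bullets concern compliance.

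- Patient compliance is given in a daily and a weekly form. The weekly form is "total weekly readings divided by total possible weekly readings".
- The provider bullet reads "HF care provider compliance for weekly readings (total weekly readings divided by the total number of possible weeks of readings").

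The provider's duty is set out elsewhere. Section 6.5 states: "The investigator or designee will review the PA pressure measurements on a weekly basis at a minimum". Appendix E makes the unit the individual patient: "All patients should be reviewed at least weekly". Section 6.7 keeps the two roles apart: "Subjects will be instructed to take daily readings and trend data will be reviewed by a healthcare professional". The Synopsis (Data Collection) draws the same distinction.

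On oversight, section 6.5 says "Weekly logins to the database will be monitored by the sponsor". No section links those logins to the compliance measure in 12.1.5.2.

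**The concern.** The two bullets are meant to describe two different actors, but nothing in the provider formula refers to anything the provider does. Followed as written, it produces the patient's weekly adherence a second time under a provider label.

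The study's stated purpose is to characterize use of the system in a real-world setting, and 12.1.5.2 sets out to characterize how well physicians and site personnel use it. Review is the step between a transmitted pressure and a treatment decision. Of the usage items listed, provider compliance is the only one intended to measure review itself. If it really measures patient adherence, a center type with adherent patients will appear to have diligent providers. A center type with diligent providers and less adherent patients will appear to have poor ones.

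**Working it through.** The plan gives no figure for provider compliance, so there is nothing to reproduce. The check is a term-by-term comparison followed by an illustration.

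**Step 1: compare the formulas (12.1.5.2).**

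- Numerator: the wording is identical in both bullets, a total of weekly readings.
- Denominator: possible weekly readings for the patient, possible weeks of readings for the provider. If each week offers one possible weekly reading, these are the same count.
- Provider action: absent from both.

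**Step 2: settle what a reading is.** In section 6.7 and the Synopsis the subject takes readings and the professional reviews trend data. In section 6.5 the investigator or designee reviews measurements. On that usage the shared numerator counts weeks with a patient reading.

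**Step 3: apply both definitions to one subject.** The 52 possible weeks are an assumption. Let *p* be the weeks with a patient reading and *r* the weeks in which a provider reviewed that subject's pressures.

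- Provider compliance as written = *p*/52
- Review-based compliance = *r*/52

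| *p* | *r* | Patient weekly | Provider, as written | Review-based |
|---|---|---|---|---|
| 52 | 52 | 100% | 100% | 100% |
| 52 | 26 | 100% | 100% | 50% |
| 52 | 0 | 100% | 100% | 0% |
| 26 | 26 | 50% | 50% | 50% |
| 26 | 52 | 50% | 50% | 100% |

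The third and fourth columns agree in every row because they are the same formula. The figure as written does not respond to *r*, and it can err in either direction: too high in rows two and three, too low in row five.

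**The case against.** The strongest reply is that, under a heading about provider compliance, a weekly reading may be meant as the provider's weekly reading of the data. That intention is plausible. The text does not state it, however, and the plan's usage elsewhere points the other way. Even on that meaning, no section says what counts as a review or where it would be recorded, so the measure would still need a definition.

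A second reply is that this is one descriptive item with no hypothesis or threshold and no part in the success criterion of section 12.3. It is also not the only item reported by center type: hospitalization rates, medication changes with reasons, and patient compliance are there too. This stands, and it limits the consequence.

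Several stronger readings are tempting but unsupported:

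- *Logins are the only provider activity tracked.* They are not. Medication changes are reported with reasons, including pressure-guided ones (Synopsis, section 6.7). The Subject Contact Log and Structured Interview (Appendices K and L) record calls prompted by pressures and their outcome. What these do not record systematically is a review that led to no contact or change, and none of them feeds the formula.
- *One site login would count as review of all that site's subjects.* Section 6.5 sends reminders to sites, but does not say whether logins are counted by site, user or subject, and does not make them the source of this measure.
- *Reminders inflate the figure.* Section 6.5 says "Reminders will be sent to the clinical sites if there are no logins noted during the course of a 7-day window". Logins do not enter the formula as written, so the formula gives no basis for this.
- *Weekly is the wrong yardstick because Appendix E lists more frequent review for some states.* That table gives a recommended frequency, while weekly is the stated minimum for everyone. Scoring against the minimum is not an error.

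**Conclusion.** The provider-compliance formula is wrong as written, not merely short of detail: taken literally, it returns patient weekly adherence under a provider label. In the illustration the discrepancy runs from 100% reported with no review to 50% reported with complete review. Those values rest on the assumed 52 weeks, on one possible weekly reading per week, and on *readings* keeping the meaning it has elsewhere in the plan.

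The effect is confined to a descriptive additional analysis, where the comparison of provider use by center type would be mislabelled. The two primary safety tests, their power, the transmission-success endpoint and the secondary hospitalization analysis do not use this quantity. A reader might infer that the plan will in practice report full provider compliance where nobody looked at the data. The documents show only that the stated rule would allow it. They do not show how the sponsor will program the measure or what the website records.

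**What to change.** Redefine the measure in 12.1.5.2:

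- **Numerator:** subject-weeks in which that subject's pressures were reviewed by the follow-up team at least once.
- **Denominator:** subject-weeks from discharge to 12 months, death or exit, with a sentence on how weeks without a transmission are handled.
- **Source:** name it. A subject-level website access log would serve, if one is kept; the documents do not say whether it is.

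If only logins are recorded, label the measure login compliance and state the unit at which logins are counted. The patient-compliance bullet can stay as it is.

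Reporting review frequency against the Appendix E table, or marking weeks in which a reminder was sent, would be optional additions.

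The cost is a few lines of SAP text and one data extract, with no change to visits or patient care. The downside is that reported provider compliance may be lower than under the present formula.
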